When the last patient in a dose level cohort has completed the DLT evaluation period the SMC will evaluate available safety and PK data from that cohort. Dose escalation will proceed only if the SMC confirms that it is safe to do so.

Variables

- Safety

- AEs
- Laboratory findings (refer to Sections [4.4.1](#) and [4.7.1.2](#))
- Physical examination
- Vital signs

- Cardiac monitoring (including 12-lead electrocardiograms [ECGs] and echocardiography)
- Dermatological examinations
- Ophthalmological examinations (including visual acuity, Schirmer’s test, slit-lamp examination, pupil dilation and intraocular pressure measurements [if considered appropriate by investigator]).

For definition of DLT, refer to Section 3.1.5.

- Pharmacokinetics

PK of AZD8931 will be investigated after both single and multiple doses

- Single dose plasma PK, including area under the plasma concentration-time curve from time zero to 12 hours (AUC_{0-12}), 24 hours (AUC_{0-24}), time t (AUC_{0-t}) and infinity (AUC) after dosing, maximum plasma drug concentration (C_{max}), time to reach the maximum plasma drug concentration (t_{max}), terminal elimination half-life ($t_{1/2}$), total apparent drug clearance (CL/F), and apparent volume of distribution (V/F)
- Multiple dose plasma PK, time to ss and assessment of any accumulation of AZD8931, including AUC_{ss0-12} , C_{ssmax} , t_{ssmax} , CL_{ss}/F , minimum plasma concentration at ss (C_{ssmin}), accumulation ratio (R_{AC}) and linearity factor

Other PK parameters may be determined if deemed appropriate.

- Exploratory

- Correlation of cell death (proapoptotic) biomarkers with AZD8931 therapy (optional)
- Optional pharmacogenetic sampling (blood sample) for DNA extraction and archiving
- Objective Response Rate (ORR) and Best Overall Response (based on RECIST) for patients with measurable disease, or other measures of efficacy in patients with non-measurable disease.

Statistical methods

Outcome variables will be listed and summarised using descriptive statistics, as appropriate. No formal hypotheses will be associated with these variables.

TABLE OF CONTENTS	PAGE
TITLE PAGE	1
PROTOCOL SYNOPSIS.....	3
TABLE OF CONTENTS.....	7
LIST OF ABBREVIATIONS AND DEFINITION OF TERMS	12
1. INTRODUCTION	15
1.1 Background	15
1.1.1 Non-clinical studies	17
1.1.1.1 Pharmacology	17
1.1.1.2 Pharmacokinetics	17
1.1.1.3 Toxicology	18
1.1.2 Clinical studies.....	20
1.2 Rationale	21
1.2.1 Rationale for safety and pharmacokinetics	21

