3.1.1 Overall design

This study is an open-label, MAD, phase 1 study to explore the safety and tolerability of AZD8931.

Adult patients with advanced solid malignancies will be eligible for enrolment into this study. Written informed consent for participation in the study is required from the patient before any study specific procedures are conducted.

A minimum of 3 and a maximum of 6 eligible patients will be dosed initially. At the discretion of SMC or, if 1 patient within a dose cohort experiences a DLT, additional patients can be enrolled to ensure the cohort includes a maximum of 6 evaluable patients. Dose escalation may occur if the SMC declares the dose level as tolerable (as detailed in Section 3.1.2 for dose escalation and recruitment procedures). The dose will initially be escalated by dose doubling, up to a level where the SMC decide that smaller escalation steps are warranted. Based on emerging data, including PK and/or safety data and/or pre-clinical data, the SMC can consider alternative schedules, including once-daily dosing of AZD8931, in consultation with AstraZeneca and . There will be adequate time between dose groups to allow review of relevant safety and PK data by the SMC.

Hospitalisation of patients (for safety monitoring or convenience) is at the discretion of the investigator, although the patients should remain at the clinic until completion of the 12 hour post-dose assessments.

Each of the cohorts may remain open until a maximum of 6 patients within the cohort have been defined as evaluable for the dose escalation set (see Table 4), and thereafter further recruitment into that cohort may be closed pending a decision about dose escalation. At the discretion of the SMC, in order to explore any safety concerns in the absence of DLT, each dose level cohort may be expanded to include a maximum of 6 patients who are evaluable for the dose escalation set.

The study design is presented in Figure 2 and the study plan is presented in Table 1.

Patients will have the option to provide a blood sample for genotyping after confirmation of eligibility. Patients who agree to take part in this genetic research will be asked to sign a separate informed consent form to confirm their willingness to have this sample taken. The samples will be stored and may be analysed in future research. See Appendix G for further details on the pharmacogenetics research planned in this study.

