3.1.2 Criteria to conduct dose escalation

The DLT evaluation period starts from the first administration of AZD8931 and continues until the completion of all assessments prior to cycle 2. For patients who continue beyond cycle 1, the DLT evaluation period ends following the completion of pre-dose assessments on the first day of cycle 2 (ie R1 cycle 2). For those patients who do not proceed beyond cycle 1 the DLT evaluation period ends following the completion of all assessments on the last day of cycle 1. Following cycle 1, subsequent treatment cycles are continuous. Dose reductions are not permitted during the DLT evaluation period, except following a DLT. If dosing of AZD8931 needs to be interrupted due to intolerable toxicities, then the DLT evaluation period may extend by the appropriate duration. Dose omissions for any other reason must not extend the DLT evaluation period. Evaluability of such patients will depend on meeting the description of analysis sets as described in Table 4 (Section 6.4.3). The cohorts may remain open until a maximum of 6 patients within the cohort have been defined as evaluable and thereafter further recruitment into that cohort will be closed pending a decision from the SMC.

Prior to each dose escalation, the SMC (see Section 6.6) will meet to review the available safety, tolerability (including AEs, laboratory assessments, ophthalmic assessments, physical examinations, vital signs, cardiac monitoring parameters) and PK data. The dose escalation decision will be documented and the minutes will be distributed to each site.

[figure not shown]
Throughout the study, dose escalation decisions will be based on a minimum of 3 and a maximum of 6 evaluable patients per dose cohort (see 'dose escalation evaluable set' described in Table 4). If a patient has received less than 80% of the defined dose and this is due to toxicity, a discussion will take place between AstraZeneca and the investigator to determine if this is a DLT. Replacement patients will enrol until the minimum required number of evaluable patients is available for assessments – see Section 3.4.4 for information on replacement of patients. Reasons for patient withdrawal will be given due consideration when enrolling replacement patients.

The SMC will review the data from each of the patients who completed the DLT evaluation period and decide if dose escalation is appropriate according to the following criteria:

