- If DLT is observed in ≥ 2 patients within the DLT evaluation period then this dose will be declared as non-tolerated and dose escalation will stop. A lower dose may be investigated at the discretion of the SMC (Section 6.6).
- If during the DLT evaluation period a DLT is observed in 1 patient within a dose level cohort consisting of less than 6 evaluable patients, additional patients will be recruited, to maintain a maximum of 6 evaluable patients in the cohort
- If during the DLT evaluation period there are no DLTs observed within a dose level cohort, containing 3 to 6 patients evaluable for the presence of DLT, then the dose will be defined as tolerable and dose escalation will continue with an incremented increase in a new group of at 3-6 patients.

Figure 1 summarises the rules to be applied.

Figure 1 Phase I dose escalation decision tree

Footnotes:

Patients in the above schematic refer to evaluable patients (dose escalation set).

^a At the discretion of the SMC, in order to explore any safety concerns in the absence of DLT, each dose level cohort may be expanded to include a maximum of 6 patients who are evaluable for the dose escalation set.

Abbreviations: DLT: dose-limiting toxicity, MTD: maximum tolerated dose

The dose will initially be escalated by dose doubling, up to a level where the SMC decide that smaller escalation steps are warranted, based on PK and/or safety data. If the exposure in patients is more than 10% to 15% greater than predicted based on data obtained in healthy subjects, the dose escalation may proceed in a more conservative manner. The SMC will determine the dose escalation based on the above criteria at the end of each dose group.

Based on emerging data, including PK and/or safety data and/or pre-clinical data, the SMC can consider alternative schedules, including once-daily dosing of AZD8931, in consultation with AstraZeneca and

When a non-tolerated dose is defined, dose escalation will be stopped and the MTD will be confirmed (see Section 3.1.4).

Following each dose decision, the patients already receiving study medication may remain on treatment at their original dose if, in the opinion of the investigator, the patient is receiving some benefit from therapy, is free from intolerable toxicity and does not meet one of the discontinuation criterion listed in Section 3.3.5.1.

Intra-patient dose escalation is not permitted.

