6.4.3 Description of analysis sets

Three patient analysis sets will be used as defined in Table 4; the safety set, the dose escalation evaluable set and the PK evaluable set. The primary analysis set will be the dose escalation evaluable set.

Table 4 **Definition of analysis sets**

Analysis set	Definition
Safety set	This population comprises all patients entered into the study who received at least one dose of AZD8931
Dose escalation evaluable set*	All patients in the safety set who have either experienced a DLT, or received at least 80% of planned doses of AZD8931 and who had all safety assessments completed during the DLT evaluation period
PK evaluable set	All patients in the safety set who have Day D1 PK data and/or have Day R14 PK data (and have received all doses during the day before Day R14)

*The SMC decide evaluability in the absence of appropriate assessments

Rules for identification of significant protocol violations will be given in the SAP. If a substantial number of patients are deemed to be protocol violators a separate ‘per-protocol’ analysis set will be determined, prior to analysis, which will exclude these patients.

6.4.4 **Methods of statistical analyses**

6.4.4.1 **Pharmacokinetic data**

The PK analysis is described in Section 6.1.1. The PK endpoints will be listed for individual subjects and summarised by dose level.

6.4.5 **Determination of sample size**

No formal sample size calculations were performed since the study follows a 3+3 dose group dose escalation design (see Section 3.1.2).

6.5 **Interim analyses (Not applicable)**

No interim analyses are planned.

6.6 **Data monitoring committee**

Working rules of the SMC are described in the SMC charter.

The SMC will comprise:

- The principal investigators of all sites
- The AstraZeneca physician
- The Medical Monitor.

In each case at least one deputy may be nominated.

On a case-by-case basis, the SMC may seek advice from further experts, including qualified representatives of AstraZeneca/

Following completion of the DLT period by ≥ 3 evaluable patients, the SMC will review all available data and decide upon dose progression. Further ‘ad-hoc’ meetings of the SMC may be convened, if required.

The safety review of data from each dose group will lead to one of 4 possible outcomes:

- Escalate to a higher dose
- Repeat dose level in further patients to obtain 6 evaluable patients at that dose level

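### Section 6.6 lets the escalation decision follow three evaluable completers, whereas the synopsis waits for the last patient in the cohort

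*Protocol*

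**What the plan says.** Two places in the protocol tie the decision to a finished cohort.

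- Synopsis, Safety Monitoring Committee: "When the last patient in a dose level cohort has completed the DLT evaluation period the SMC will evaluate" the safety and PK data. Escalation proceeds only if the committee confirms that it is safe.
- Section 3.1.2: "The SMC will determine the dose escalation based on the above criteria at the end of each dose group".

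Two places are looser.

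- Section 6.6: after the DLT period has been completed by at least three "evaluable patients, the SMC will review all available data and decide upon dose progression". It sets no condition on other patients already dosed at that level.
- Section 3.1.2, in the sentence that introduces the escalation criteria: "The SMC will review the data from each of the patients who completed the DLT evaluation period".

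Cohort size is flexible. Section 3.1.1 states: "A minimum of 3 and a maximum of 6 eligible patients will be dosed initially". Section 3.1.2 adds: "The cohorts may remain open until a maximum of 6 patients within the cohort have been defined as evaluable". With no DLT among 3 to 6 evaluable patients, Section 3.1.2 says "then the dose will be defined as tolerable and dose escalation will continue". The next step may be as large as a doubling (Section 3.2.1).

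**The concern.** The two triggers coincide only when exactly three patients are dosed. If four, five or six are dosed, the third can finish while the others are part-way through. An event-free patient in mid-window is not yet evaluable under Table 4, because the required doses and safety assessments are not complete. The Figure 1 footnote limits the decision tree to evaluable patients. A cohort with three clean completers and up to three pending patients therefore meets the no-DLT criterion as written, and neither Section 6.6 nor that criterion tells the committee to wait.

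What is at stake is interim exposure: new patients could start a dose up to twice as high before the outcome of patients already treated at the current dose is known. Interim data on the pending patients may be thin for some toxicities. After screening, Table 1 next schedules the full eye examination and echocardiography at R21 or premature discontinuation. Symptoms prompt earlier eye examination or echocardiography, but the LVEF criterion in Section 3.1.5 needs no symptoms.

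**Working it through.** The protocol states no operating characteristic for this decision (Section 6.4.5 gives no formal calculation), so there is no figure to reproduce. The sizes below illustrate the literal reading of Section 6.6.

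**Inputs**

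- Decision after three completers with no DLT: Sections 6.6 and 3.1.2.
- Non-tolerated means 2 or more DLTs (Section 3.1.3). One DLT in six is taken as tolerated (Sections 3.1.3 and 3.1.4).
- One DLT in a cohort of fewer than six leads to expansion: "DLT is observed in 1 patient within a dose level cohort consisting of less than 6 evaluable patients, additional patients will be recruited" (Section 3.1.2).
- Number dosed: 4, 5 or 6, so 1, 2 or 3 patients are pending.
- DLT risk p: **assumed** 20%, 30%, 40%, because the documents give none. Write q = 1 − p.

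The chance of a clean first three is q³ = 0.512, 0.343, 0.216.

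**Event sized:** escalation on 0/3 from a dose that shows 2 or more DLTs once its cohort reaches six.

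*Upper bound: nothing is known about the pending patients.*

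- 4 dosed: the pending patient has a DLT and at least one of two added patients does too: q³ · p · (1 − q²).
- 5 dosed: both pending patients have a DLT, or one does and the sixth patient does: q³ · (p² + 2pq · p).
- 6 dosed: at least two of three pending patients have a DLT: q³ · (3p²q + p³).

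For example, at p = 0.3 with 6 dosed: 0.343 × (3 × 0.09 × 0.7 + 0.027) = 0.343 × 0.216 = 0.074.

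*Half the window observed: onset is uniform, and any DLT already seen blocks escalation.* A DLT still to come then has probability u = p/2 per pending patient.

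- 4 dosed: q³ · u · (1 − q²).
- 5 dosed: q³ · (u² + 2uq · p).
- 6 dosed: q³ · (3u²q + u³).

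For example, at p = 0.3 with 6 dosed: 0.343 × (3 × 0.0225 × 0.7 + 0.003375) = 0.343 × 0.050625 = 0.017.

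| Dosed | Upper bound, p = 20% / 30% / 40% | Half window observed, p = 20% / 30% / 40% |
|---|---|---|
| 3 | 0 / 0 / 0 | 0 / 0 / 0 |
| 4 | 3.7% / 5.2% / 5.5% | 1.8% / 2.6% / 2.8% |
| 5 | 5.3% / 7.4% / 7.6% | 2.2% / 2.9% / 2.9% |
| 6 | 5.3% / 7.4% / 7.6% | 1.3% / 1.7% / 1.7% |

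With 6 dosed, the upper bound is 2.0% at p = 10%, 7.7% at 33% and 6.3% at 50%, so about 8% is a ceiling over that wider range as well.

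**A broader event.** Escalating on 0/3 when the dosed cohort would have called for expansion or stopping is more frequent. The upper bound is q³p = 10%, 10%, 9% with 4 dosed and q³(1 − q²) = 18%, 17%, 14% with 5 dosed. The part above the table is escalation that expansion to six would only have delayed, so it does not measure a wrong decision.

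**Length of the window.** Dosing starts on Day 1, R1 falls on Day 5 to 7, and R21 on Day 25 to 27. The cycle 2 pre-dose assessments come the next day. A window therefore lasts 25 to 28 days.

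**The case against.** The strongest reply is that the protocol already states the trigger. The synopsis rule is explicit. Section 3.1.2 speaks of the end of the dose group, and the Figure 2 flow chart puts data review and the committee meeting between one group's dosing and the next group's first dose. Section 3.2.1 provides time between groups for collecting and reviewing data. On that view Section 6.6 only restates the minimum of three evaluable patients; it does not say that the decision falls as soon as the third completes, and it goes on to refer to each dose group. The SMC charter, which is not shown, may also settle the timing.

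Much of this stands. A reader might infer that the protocol mandates escalation over pending patients, or that its sections cannot be reconciled. The documents do not support either: three can be read as a floor within a finished group. What remains is that Section 6.6, which sets out the committee's review and its outcomes, does not repeat the waiting condition, and the rule it feeds says that escalation will continue.

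The safeguards also count. All available data are reviewed, and the decision is by consensus of a committee that includes every site's principal investigator. A DLT already seen in a pending patient makes that patient evaluable under Table 4. These lower the risk but do not make the decision wait for patients who are event-free and unfinished. It is also fair that 0/3 is the design's accepted evidence for escalating from a cohort of exactly three. The point here is narrower: outcomes of patients already on drug would be left out.

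**Conclusion.** The concern holds as an inconsistency in the trigger, worth correcting because it bears on patient safety and is cheap to remove. The excess risk is small: about 1% to 3% with half of each pending window observed, at most about 8% with nothing known, and zero with exactly three dosed. These figures rest on assumed DLT risks of 20% to 40% and on the literal reading of Section 6.6. The half-window figures also assume uniform onset, which may be optimistic for toxicities looked for mainly at R21.

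A reader might infer that the MTD itself could be wrong. The documents do not support that. Late DLTs still make the dose non-tolerated under Section 3.1.3, and Section 3.1.4 still requires confirmation at the dose below. The harm is limited to patients who start the next dose in the interval.

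**What to change.** In Section 6.6, and in the review sentence of Section 3.1.2, carry over the synopsis rule, for example:

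> Three evaluable patients is the minimum for an escalation decision. No escalation decision is made until every patient already dosed at that level has completed the DLT period, had a DLT, or been declared non-evaluable.

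This restricts escalation only. Stopping at two DLTs need not wait, and enrolment need not be paused, since Sections 3.1.1 and 3.1.2 deliberately let a cohort stay open until six are evaluable.

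The cost is a wording change in two places, and in the SMC charter if it repeats Section 6.6. When more than three patients are dosed, the decision usually waits up to one further window of 25 to 28 days. It can be longer if a toxicity interruption extends a patient's window: Section 3.1.2 sets no limit on the extension, and Section 3.4.3 allows up to 21 days for a toxicity to resolve.

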7. ETHICS

7.1 Ethics review

AstraZeneca will provide Central Ethics Committees and Regulatory Authorities with safety updates/reports according to local requirements. Investigators and local Ethics Committees will receive this information from

The final study protocol, including the final version of the Informed Consent Form, must be approved or given a favourable opinion in writing by an Ethics Committee as appropriate. The investigator must receive written approval before he or she can enrol any patient into the study.

The principal investigator is responsible for informing the local Ethics Committee of any amendment to the protocol in accordance with local requirements. In addition, the Ethics Committee must approve all advertising used to recruit patients for the study. The annual report must be submitted to the Ethics Committee annually, as local regulations require.

Where there is a genetic research, approval must be obtained for this genetic research and the associated genetic informed consent from the Ethics Committee. It must be clearly stated in the approval that this genetic research is approved. The investigator must receive written approval before any patient participates in this genetic research.

7.2 Ethical conduct of the study

The study will be performed in accordance with the ethical principles that have their origin in the Declaration of Helsinki and are consistent with GCP, applicable regulatory requirements and the AstraZeneca policy on Bioethics.

7.3 Informed consent

The principal investigator at each centre will ensure that the patient is given full and adequate oral and written information about the nature, purpose, possible risk and benefit of the study. Patients must also be notified that they are free to discontinue from the study at any time. The patient should be given the opportunity to ask questions and allowed time to consider the information provided.

The patient's signed and dated informed consent must be obtained before conducting any procedure specifically for the study.

The principal investigator must store the original, signed Informed Consent Form. A copy of the Informed Consent Form must be given to the patient.

If modifications are made according to local requirements, the new version has to be approved by AstraZeneca.

The exploratory biomarker analysis is optional and the patient may participate in the main study without participating in this component. To participate in this component of the study the patient must sign and date the consent forms for both the main study and the biomarker component of the study. Copies of signed and dated consent forms must be given to the patient and the original filed at the study centre. The principal investigator(s) is responsible for ensuring that consent is given freely and that the patient understands that they may freely discontinue this aspect of the study at any time.

The genetic research is optional and the patient may participate in the main study without participating in the genetic component. To participate in the genetic component of the study the patient must sign and date the consent forms for both the main study (non-genetic components of the study) and the genetic component of the study. Copies of both signed and dated consent forms must be given to the patient and the original filed at the study centre. The principal investigator(s) is responsible for ensuring that consent is given freely and that the patient understands that they may freely discontinue the genetic aspect of the study at any time.

If modifications are made to the master Informed Consent Form, according to local requirements, the new version has to be approved by AstraZeneca.

